Early Gestational Diabetes Screening in Gravid Obese Women

(EGGO)

Protocol

(Version 1.1; 02.17.2014)

Study Procedures

1. **Screening.** Records of health clinic patients will be reviewed by trained research staff to identify eligible patients. Eligible patients will receive a letter and/or phone call notifying them of their eligibility and asking them to participate. Trained research staff will be available at the OB Complications clinic and ultrasound to **screen** and **consent** patients. A screening log or form will be used to track all patients approached for the study. Women will be randomized at the time of consent. At the time of consent, women will sign a maternal/infant medical record release which will be faxed to any hospitals to obtain records for review if necessary.
2. **Randomization.** A confidential, computer-generated simple randomization scheme will be prepared by a designated study biostatistician. Randomization will be stratified by morbid obesity (BMI>40.0). Women will be randomized after they give consent by pulling the next sequential envelope from the participant's BMI group that will disclose whether the participant is assigned to early or routine timing of the GDM screen.
3. **Gestational Diabetes Screening.**
 - a. **Early Screening Group.**
 - i. Women assigned to "early screening" will complete the BSST (50-g glucose load) between 14 weeks, 0 days gestation and 20 weeks, 0 days gestation. If the test cannot be completed due to nausea or vomiting, the patient may choose to re-schedule another attempt prior to 20 weeks, 0 days or she may choose to withdraw from the study.
 1. If a participant is between 14 weeks, 0 days and 20 weeks, 0 days at the time of randomization she may:
 1. Choose to undergo BSST at the time of randomization in OBCC clinic. Add EGGO to her problem list with a message that she was randomized to early screening & the date of completion of the BSST.
 2. Choose to undergo BSST at next appointment at her local clinic. If she chooses this option, place a message in IMPACT and EGGO to her problem list with her randomization group. This will notify her provider to complete the BSST at the next visit prior to 18 weeks.
 - ii. At the time of the BSST, a purple and gold top tube will be drawn for HbA1c & Glycomark (refer to baseline procedures below). These specimens will be labeled with the patient name plate and sent to the OBGYN lab for testing.

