- ii. Women who are not diagnosed with GDM (i.e. women who have a normal 1-hour BSST or who have an elevated 1-hour BSST but a normal 3-hour GTT) will continue routine prenatal care.
- iii. Women who are diagnosed with GDM will enter into routine GDM care with dietary counseling and patterned blood sugars.

5. Baseline Procedures

- Measurement of height, without shoes, at time of enrollment.
- Record self-reported prepregnancy weight.
- All women will have a blood draw for HbA1c and Glycomark between 14 weeks, 0 days and 20 weeks, 0 days gestation. The blood for HbA1c should be collected in a purple top tube (3mL). The blood for Glycomark should be collected in a gold top tube (3mL).
 - Women undergoing early GDM screening may have these blood samples drawn at the time of the blood draw for the 1-hour BSST.
 - Women randomized to routine screening may have these blood samples drawn at the time of randomization if between 14 weeks, 0 days and 20 week, 0 days. Otherwise, they may have the blood drawn at their clinic at an appropriate time (i.e. at the time of other routine prenatal lab draws).
 - Samples will be labeled with patient name plate for transport to OBGYN lab.
 - Samples may be stored at room temperature or 4°C (refrigerated) for up to 7 days.
- All women will have a blood draw for HbA1c and Glycomark between 24 weeks, 0 days and 28 weeks, 0 days gestation. The blood for HbA1c should be collected in a purple top tube (3mL). The blood for Glycomark should be collected in a gold top tube (3mL).
 - This blood draw may be performed at the time of the 1-hour BSST.
 - Women diagnosed with GDM prior to 24-28 weeks may have the blood drawn in clinic at the appropriate gestational age, in conjunction with routine prenatal lab draws or separately.
 - Samples will be labeled with patient name plate for transport to OBGYN lab.
 - Samples may be stored at room temperature or 4°C (refrigerated) for up to 7 days.
- Trained and experienced research staff in obstetric and perinatal outcomes abstraction will be responsible for all research data abstraction from patient medical records.
- Maternal outcomes will be ascertained in the hospital following delivery and at the routinely scheduled follow-up visit at 4-6 weeks after delivery.
- Newborn outcomes will be ascertained until 6 weeks after delivery through maternal questioning regarding re-admission. Readmissions for infants will be validated through medical review.

6. Follow-up

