- a. Women with gestational diabetes will be contacted prior to their appointment by either phone or letter to remind them to come to their post-partum visit prepared for the fasting, 2-hour, 75-g glucose tolerance test.
- b. Women diagnosed with gestational diabetes will undergo a 2-hour, 75-g glucose tolerance test at the time of their post-partum visit at OBCC or resident continuity clinic. They will receive \$10 for undergoing this testing.
- c. All women will be asked whether they or their infant have been re-admitted to the hospital since the time of discharge and the reason for admission. Permission will be obtained to request records for re-admission diagnoses.

7. Outcome Measures

The primary outcome will be a composite outcome of macrosomia (birth weight >4000g), primary cesarean, gestational hypertension or preeclampsia, shoulder dystocia, neonatal hyperbilirubinemia, and neonatal hypoglycemia. Each of these outcomes will also be evaluated individually as secondary outcomes. Additional secondary outcomes will include premature delivery (<37wks).

- a. Macrosomia: Will be defined by measurement of infant birth weight. Macrosomia is a birth weight >4000 g.
- b. Primary cesarean: A primary cesarean delivery for any indication will be considered as having the outcome of interest.
- c. Gestational hypertension: Defined by systolic blood pressure ≥ 140 or diastolic blood pressure ≥ 90 without proteinuria (urine protein/creatinine ratio < 0.19 or 24-hour urine protein < 300 mg).
- d. Preeclampsia: Defined by systolic blood pressure ≥ 140 or diastolic blood pressure ≥ 90 with proteinuria (urine protein/creatinine ratio ≥ 0.19 or 24-hour urine protein ≥ 300 mg). Preeclampsia diagnosis will also be refined by mild or severe. Severe preeclampsia will be defined as systolic blood pressure ≥ 160 , diastolic blood pressure ≥ 110 , proteinuria ≥ 5000 mg in 24 hours or 3+ urine dip, platelets < 150 , AST > 60 , oliguria (< 500 mL urine/ 24 hours), pulmonary edema, creatinine > 1.0 .
- e. Shoulder dystocia: As documented by delivering physician; defined as requiring more than routine downward traction to achieve delivery of anterior shoulder. The length of the shoulder dystocia and maneuvers required to relieve the shoulder dystocia will be documented.

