- f. Neonatal hyperbilirubinemia: Neonatal bilirubin levels will be recorded. Hyperbilirubinemia will be defined $> 95^{\text{th}}$ percentile gestational age and hour of life. The treatment of hyperbilirubinemia (i.e. phototherapy) will also be recorded.
- g. Neonatal hypoglycemia. Blood sugar levels will be abstracted from neonatal charts. Neonatal hypoglycemia will be defined as blood sugar < 35 mg/dL.

8. Data Collection Form Definitions

- a. Randomization Form
 - i. Age at the time of presentation
 - ii. Body mass index as defined by self-reported pre-pregnancy weight & measured height
 - iii. Gestational age <20 weeks, 0 days as defined by earliest documented ultrasound
 - iv. Known history of diabetes mellitus by patient report or as documented in clinical records
 - v. Major medical illness
 - 1. Chronic/daily prednisone use
 - 2. On home oxygen
 - 3. Prior cardiac surgery
 - 4. History of cardiomyopathy, valvular stenosis, pulmonary hypertension
 - 5. History of any transplanted organ
 - 6. HIV/AIDS
 - 7. Hemoglobinopathy (i.e. sickle cell disease)

Conditions not considered a major medical illness:

 - 1. Chronic hypertension
 - 2. Asthma (unless requiring prednisone on daily basis)
 - 3. Obstructive sleep apnea (unless requiring home oxygen)
 - vi. Unable to provide informed consent
 - 1. Language barrier
 - 2. Prisoner
 - 3. Mental illness
 - 4. Judgment of person performing enrollment
 - vii. Known fetal anomalies
 - 1. Structural anomalies (heart defect, brain defect, renal anomaly, abdominal wall defect) or known fetal aneuploidy by karyotype or non-invasive prenatal diagnosis
 - 2. Soft markers of aneuploidy are not exclusion criteria (echogenic intracardiac focus, choroid plexus cyst, renal pelvis dilation/pyelectasis)
 - viii. History of bariatric surgery
 - 1. Either banding procedure or Roux-en-Y
 - ix. Multifetal gestation
 - x. Prior cesarean
- b. Enrollment Form
 - i. Measured height without shoes

- ii. Self-reported pregnancy weight obtained from patient interview at time of enrollment
 - iii. History may be obtained from patient directly or from chart
 - iv. Exam at time of enrollment
- c. Diabetes Testing Form
 - i. Document Randomization group
 - ii. Document date and value of BSST, GTT, HbA1c, and Glycomark
- d. Prenatal Care Data Collection Form
 - i. Document whether exclusion criteria developed during course of prenatal care
 - ii. Record number of prenatal visits and date, weight, and blood pressure each visit.

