 - iii. Document date, indication, estimated fetal weight, and amniotic fluid index of each ultrasound.
 - iv. Document date and type of antenatal testing performed, & indication for test.
 - v. Document all medications prescribed for gestational diabetes. Date started, the starting dose & frequency, the stop date, and the highest dose reached.
 - vi. Review other medications and document that there are no changes in medications or update medication list
- e. Blood Sugar logs
 - i. Record blood sugar logs patient provided. Date, fasting blood sugar, post-prandial blood sugar after each meal, and 21:00 & 3:00 AM blood sugar if documented.
- f. Delivery Data Collection Form
 - i. Date of admission
 - ii. Admitting diagnosis as documented by admitting physician history & physical
 - iii. Admission vital signs and labs as documented by the first vital signs and labs obtained on day of admission
 - iv. Gestational diabetes type
 - v. Blood sugar log & insulin drip as per IMPACT records
 - vi. Type of labor as documented by admitting physician history and physical
 - vii. Indication for induction of labor based on documentation by admitting physician history & physical
 - viii. Indication for scheduled cesarean as documented by admitting physician history & physical
 - ix. Medications received during labor: Check all that apply. Any medication received between the time of admission and delivery should be checked.
 - x. Record the mode of delivery, indication for operative delivery, shoulder dystocia, laceration/episiotomy, as documented by physician labor and delivery note. If information not documented by physician labor and delivery note, use nursing notes to complete information.

- xii. Post-partum hematocrit – Either spun hematocrit or hematocrit from CBC at 12 hours post-delivery.
- xiii. Endometritis as documented by caring physician.
- g. Neonatal Form
 - i. Highest level of neonatal resuscitation in delivery room as documented by caring pediatricians
 - ii. Admitting diagnosis for infant to nursery as documented by pediatricians admission note
 - iii. Cause of death as documented by expiration summary
 - iv. Neonatal injuries as documented by pediatrics admission note & daily notes prior to discharge
 - v. Method of feeding as documented by nursing notes/pediatricians notes
- h. Post Partum
 - i. Readmission of mother to hospital after initial discharge – obtain by questioning mother and obtain confirmation with records request

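### Nothing in the plan keeps the arm from the staff who abstract outcomes, which matters mainly for the hypertension and preeclampsia component of the composite

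*Protocol*

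**What the plan says.** **Who abstracts.** Protocol section 5: "Trained and experienced research staff in obstetric and perinatal outcomes abstraction will be responsible for all research data abstraction from patient medical records". No masking condition is attached. Neither document mentions masked abstraction, masked adjudication or an endpoint committee. The only reference to blinding, in Protocol section 3.b, concerns the routine-arm HbA1c result.

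**Where the arm is visible.**
- Protocol section 2: the envelope "will disclose whether the participant is assigned to early or routine timing of the GDM screen".
- Protocol section 3.a, early-arm woman tested at randomization: "Add EGGO to her problem list with a message that she was randomized to early screening".
- Protocol section 3.a, early-arm woman tested later at her local clinic: "place a message in IMPACT and EGGO to her problem list with her randomization group".
- Protocol section 8.c, Diabetes Testing Form: "Document Randomization group". The next item on that form asks for the dates and values of the glucose tests, and the dates also reveal the arm.

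**How components are scored.** Under SAP 3.1.1, one positive component makes the composite positive.
- Shoulder dystocia (Protocol 7.e): "As documented by delivering physician; defined as requiring more than routine downward traction to achieve delivery of anterior shoulder".
- Source order for delivery items (Protocol 8.f.x): "If information not documented by physician labor and delivery note, use nursing notes to complete information".
- Cesarean (Protocol 7.b): "A primary cesarean delivery for any indication will be considered as having the outcome of interest".
- Macrosomia and neonatal hypoglycemia are numeric cut-offs (above 4000 g; below 35 mg/dL).
- Hyperbilirubinemia is a value above the 95th percentile for gestational age and hour of life.
- Gestational hypertension and preeclampsia rest on a systolic pressure of at least 140 or a diastolic of at least 90, split by proteinuria. The number, spacing and timing of readings are not given.

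**The concern.** Abstractors read records that can show the arm, and nothing in the plan limits what they know. If the scoring of a component requires a choice, that choice can lean one way in one arm, without intent. Because one positive component is enough, a single borderline call can move a woman with no other component from no event to event. A net difference of a few women per hundred would then enter the primary comparison as if it were a treatment effect. Neither a larger sample nor the planned covariate adjustment removes it.

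The point is confined to the trial's own scoring. Clinicians who know the arm may also behave differently, but how outcomes are abstracted cannot change that.

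**Working it through.** **1. Which components leave the abstractor a choice**

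| Component | What fixes it | Room for abstractor judgment |
|---|---|---|
| Macrosomia | Measured birth weight | Little |
| Primary cesarean | Any indication counts | Little |
| Neonatal hypoglycemia | Glucose cut-off | Little |
| Shoulder dystocia | Delivering physician's record; nursing notes only if that is silent | Little |
| Hyperbilirubinemia | Bilirubin set against gestational age and hour of life | Some: which value, which hour |
| Gestational hypertension / preeclampsia | Blood pressure and proteinuria | Most |

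Three features leave the last row open.
- No rule says which or how many readings qualify.
- Protocol section 8.a lists chronic hypertension among the conditions that are not a major medical illness, and no rule separates it from gestational hypertension.
- The protein/creatinine cut-offs differ. Protocol 7.c and 7.d divide the two diagnoses at 0.19. SAP 3.1.1 uses below 0.19 for gestational hypertension and at least 0.30 for preeclampsia. A hypertensive woman with a ratio from 0.19 to below 0.30 has preeclampsia by the protocol's ratio, and neither condition by the SAP's. Whether she counts in the composite then depends on who resolves the conflict.

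**2. The plan's own figures**

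SAP 3.1.3 has 50% against 25%, two-sided alpha 0.05 and 80% power. The pooled-variance formula without continuity correction gives 58 per group, as stated. Then 58 / 0.10 = 580 per group and 2 × 580 = 1,160. The final-look limit in SAP 3.2 is chi-square 3.91; √3.91 = 1.977, which is a two-sided p of 0.048, also as stated.

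**3. Illustration of a scoring lean**

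From the documents: n = 580 per arm and the limit 1.977. Assumed: no true effect, a composite rate p₁ = 0.50 in all randomized women, and a net lean b, so that p₂ = 0.50 − b.

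- Pooled standard error: SE₀ = √[2·p̄(1 − p̄)/n], where p̄ is the mean of p₁ and p₂
- Unpooled standard error: SE₁ = √[(p₁(1 − p₁) + p₂(1 − p₂))/n]
- Rejection probability: 1 − Φ[(1.977·SE₀ − b)/SE₁] + Φ[(−1.977·SE₀ − b)/SE₁]

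For b = 0.02: SE₀ = 0.02936, SE₁ = 0.02935 and 1.977·SE₀ = 0.05805. The two arguments are (0.05805 − 0.02)/0.02935 = 1.296 and (−0.05805 − 0.02)/0.02935 = −2.659. The tail areas are 0.0974 + 0.0039 = 0.101.

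| Net lean b | Women per arm (580·b) | False-positive rate |
|---|---|---|
| 0 | 0 | 4.8% |
| 1 point | 5.8 | 6.1% |
| 2 points | 11.6 | 10.1% |
| 3 points | 17.4 | 17.1% |

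With p₁ at 40% or 56% the results stay within 0.01 of these (for 3 points, 17.8% and 17.2%).

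**The case against.** A reader could fairly say that the composite is mostly numeric or documented by clinicians, so an abstractor mainly transcribes. That stands for birth weight, cesarean, neonatal glucose and shoulder dystocia. The nursing-note fallback is a fixed order of sources, which narrows discretion.

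Four stronger readings are tempting, and the documents do not support them.
- *That abstractors are known to be unmasked, or that the same person enrols and abstracts.* The documents are silent. Research staff screen and consent, and research staff abstract, but the protocol does not say that they are the same individuals or who pulls the envelope.
- *That the case forms in general carry the arm.* One listed form does, and it scores no component. The listed items of the Delivery and Neonatal forms do not include it. The chart entry for early-arm women is the more important leak, because abstractors work from medical records.
- *That the planned composite rate is 50%.* SAP 3.1.3 gives 56%, taken down to 50%, for obese women with GDM and for four outcomes. No rate is given for the six-part composite in all randomized women.
- *That a lean could never be found afterwards.* The sources are medical records, so a second reader without knowledge of the arm could re-abstract a sample.

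It is also fair to say that the loose hypertension rules are a definition gap that masking alone would not close. That stands, and it is why the remedy includes rules and programmed derivation. Some raw values are already collected: blood pressure at each visit, admission vital signs and labs, and bilirubin and glucose levels. But neither document says that the components are derived from them by program.

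**Conclusion.** The concern holds in a limited form. The arm is disclosed at enrolment, recorded on one form and written in the chart for early-arm women. Nothing in either document keeps it from the staff who abstract all outcome data. The exposure lies mainly in classifying gestational hypertension and preeclampsia, and to a lesser degree in matching bilirubin to hour of life.

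The size of any lean cannot be derived from the documents. The rise from 4.8% to about 6%, 10% or 17% is an illustration. It rests on an assumed lean of 1 to 3 points, net of women who are already positive on another component, and on an assumed 50% rate. It shows that the final test is sensitive to small scoring differences, not that such differences will occur. Only false positives were computed. The point merits a change because the remedy is cheap.

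**What to change.** 1. Have the Delivery and Neonatal forms abstracted by existing research staff who did not enrol that woman. They should work from the delivery and neonatal records, without the Randomization and Diabetes Testing forms.
2. Record raw values: blood pressures with dates, urine protein, birth weight, bilirubin with hour of life, and neonatal glucose. Derive each component and the composite by a program that does not use the arm. Take shoulder dystocia as documented by the delivering physician.
3. Before writing that program, reconcile the protein/creatinine cut-offs in Protocol section 7 and SAP 3.1.1, and state which blood pressure readings count.

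Deleting the arm field from the Diabetes Testing Form would gain little by itself, because the test dates on the same form reveal the arm.

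**Cost.** A rule on who receives which forms, slightly more data entry, and some programming. The first step uses existing staff, though the documents give no staffing numbers to confirm that this is workable at both sites. Masking will be partial, because the chart can still reveal the arm. Programmed derivation is therefore the more useful step, since it removes most yes/no calls even where masking fails.

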## EGGO STATISTICAL ANALYSIS PLAN

### 1. INTRODUCTION

Over 1/3 of reproductive age women are obese. Obese women have higher rates of poor pregnancy outcomes including stillbirth, fetal growth problems, diabetes, hypertension, and maternal death. Gestational diabetes (GDM) is a frequent pregnancy complication in obese women and is associated with increased risk of large infants, cesarean delivery, and high blood pressure. Although treatment of GDM improves these outcomes, obese women seem to benefit less from treatment than non-obese women. This is perhaps because obese women develop GDM earlier in pregnancy than normal weight women, leading to the baby being exposed to elevated blood sugars for a longer period prior to diagnosis and treatment.

The purpose of this study is to determine if screening obese women for gestational diabetes early in their pregnancy (at 14-20 weeks) improves pregnancy outcomes compared to screening obese women for gestational diabetes at the routine time (24-28 weeks). This study was created at UAB and will enroll 1,160 obese women at two study sites: UAB and Ochsner (New Orleans, LA). A confidential, computer-generated randomization scheme will be prepared by a designated study biostatistician. Randomization will be stratified by morbid obesity ( $BMI \geq 40.0$  vs  $BMI < 40$ ). Randomization will also be stratified for both participating sites.

### 2. DESCRIPTIVE STATISTICS

Patient characteristics at randomization will be summarized by randomization group. The two study groups will be labeled as Early (for early gestational diabetes screening 14-18 weeks) and Routine (for routine gestational diabetes screening 20-24 weeks). For continuous variables, means/medians and standard deviations/interquartile ranges will be reported. To assess and/or identify covariates for which adjusted sensitivity analyses might be conducted, Student t-tests will be used to compare means between study groups. Where appropriate, medians and quartiles will be reported and the Wilcoxon rank sum test will be used as an alternative comparison procedure. Categorical measures will be presented as counts and percentages and will be compared using the  $\chi^2$  tests of association to identify potential group differences. For rare outcomes such that the  $\chi^2$  test of association is not appropriate, Fisher's exact test will be used. Balance overall is expected because of the large sample size and we expect approximately 5% to be different by chance, since we are not adjusting these baseline comparisons for multiple testing. Any group characteristics that are identified as statistically significantly different between the two groups at a 0.05 level of significance will be considered as covariates in multivariable models in subsequent analyses of the primary study outcome.

